10.2. Laboratory Evaluations

All statistical analyses of laboratory values will be performed using SI units.

Clinical laboratory data and change from baseline will be summarized by the scheduled time point for the serum chemistry, hematology and urinalysis to weeks 16, 32 and 52 plus German extension weeks.

Patient incidences of change in classification with respect to the laboratory normal ranges will be summarized as shift tables.

Shift tables will show the number of patients who shift from each category of maximum (minimum) baseline observation to each category of maximum (minimum) post-baseline observation. Here categories may be low, normal, or high according to the central lab definition.

Baseline will be the last value obtained before randomization.

Chemistry and hematology data will be listed with the values outside the normal ranges flagged.

10.3. Vital Signs

Summary statistics for vital sign (systolic and diastolic blood pressure [mmHg], body temperature [°C], respiratory rate [breaths per minute] and pulse [beats per minute or bpm]) will be presented for each scheduled time point measured and for the change from baseline to each time point.

For convenience, the conversion for temperature:

Temperature (in °C) = 5/9 (Temperature [in °F]-32)

Observed results and changes from baseline to weeks 2, 4, 8, 12 and 16 will be summarized.

This document is confidential.

Observed results and changes from baseline to weeks 20, 24, 28, 32, 36, 40, 44, 48 and 52 plus German extension weeks will be summarized.

Number and percentage of patients who shift from normal/high to low (ie, treatment-emergent low) and the number and percentage of patients who shift from normal/low to high (ie, treatment-emergent high) will be displayed.

Table of Categorical Criteria for Abnormal Treatment -Emergent Blood Pressure and Pulse measurement, and Categorical Criteria for Weight Changes for Adult

Parameter	Low	High
Systolic BP (mmHG)	≤90 and decrease from baseline ≥20	≥140 and increase from baseline ≥20
Diastolic BP (mmHG)	≤50 and decrease from baseline ≥10	≥90 and increase from baseline ≥10
Pulse (bpm)	≤50 and decrease from baseline ≥15	≥100 and increase from baseline ≥15
Weight (kg)	(Loss) decrease ≥7%	(Gain) increase ≥7%

10.4. Physical Examination

Clinically significant physical examination abnormalities will be summarized at weeks 16, 32 and 52 plus German extension weeks.

Results of physical examination will be listed by patient and visit.

10.5. Special Safety Topics including Adverse Events of Special Interest

10.5.1. Eosinophilia and Eosinophil-Related Disorders

In addition to the standard laboratory analysis (Section 10.2), eosinophilia and eosinophil-related AEs will be summarized for the SAF. Details regarding eosinophil-related PTs are described in the separate Almirall Safety Topics of Interest.

A shift table summarizing the number and percentage of patients within each maximum baseline category versus each maximum post-baseline category by treatment will be displayed for the SAF. The following Eosinophil categories will be considered:

Eosinophil categories: normal (<500 per microliter), mild (500 to <1500 per microliter), moderate (1500 to <5000 per microliter), severe (≥5000 per microliter).

10.5.2. Infections, Including Herpes Infections and Relevant Parasitic Infections

Infections will be defined using the PTs from the MedDRA Infections and Infestations SOC. The MedDRA terms used to identify infections considered to be opportunistic infections (OI) in patients with immune mediated inflammatory conditions treated with immunomodulatory drugs are based on Winthrop et al. (2015) and are listed in the Almirall Safety Topics of Interest. The list contains narrow (more specific) and broad (less specific) PTs with respect to these prospectively defined OIs. Definitions of herpes infections, parasitic infections and skin infections are listed in the Almirall Safety Topics of Interest.

This document is confidential.

The following tables will be produced for the SAF:

- Summary of treatment-emergent infections by PT by maximum severity
- Summary of serious infections by PT
- Summary of infection AEs resulting in permanent study drug discontinuation
- Treatment-emergent potential OI by PT nested with categories for narrow terms and broad terms separately
- Treatment-emergent adverse events, herpes and parasitic infections
- Treatment-emergent adverse events, skin infection

In addition, a listing of patients with potential OI, Serious Infection, herpes and parasitic infections will be displayed.

10.5.3. Conjunctivitis

Conjunctivitis are events of special interest and will be identified using PTs nested within the categories of conjunctivitis and Keratitis as described in the Almirall Safety Topics of Interest:

The following tables and listings will be produced for the SAF:

- Summary of TEAE of conjunctivitis overall and by categories, and also describing severity, seriousness, outcome and action taken.
- Summary and/or listing of conjunctivitis and eye inflammation follow-up form
- A listing of patients with conjunctivitis

10.5.4. Hypersensitivity

Potential hypersensitivity reactions will be determined using the following Standardised MedDRA Query (SMQs): anaphylactic reaction, hypersensitivity, and angioedema. Potential hypersensitivity will be categorized as immediate (i.e., occurring the same day as drug administration) and non-immediate (i.e., occurring after the day of study drug administration but prior to subsequent drug administration).

- for immediate hypersensitivity: (1) combined narrow/algorithmic search (that is, any narrow term from any one of the SMQs, or anaphylaxis algorithm); (2) narrow search (that is, any narrow term) by SMQ; (3) TEAEs (occurring on the day of study drug administration) by PT not in any of the 3 SMQs
- for nonimmediate hypersensitivity: (1) combined narrow search (that is, any narrow term from any one of the SMQs); (2) narrow search (that is, any narrow term) by SMQ; and (3) broad search (that is, any narrow or broad term) by SMQ

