10.1. Adverse Events

Adverse events (AEs) will be coded using MedDRA Version 24.1 or higher. In the event of a missing/incomplete start or stop date associated with an adverse event, only the treatment-emergence will be imputed using the algorithm described in エラー! 参照元が見つかりません。 [section 7.3.2](#). Dates will not be imputed.

A TEAE is any AE that newly appeared, or worsened in severity following initiation of study medication until last follow-up visit. Only TEAE will be included in the summary tables, but all AE will be included in the listings.

Following tables will be produced:

- An overall summary of the number and percentage of patients reporting TEAEs, Adverse Events of Special Interest (AESI), serious TEAEs, Suspected Unexpected Serious Adverse Reactions (SUSARs), TEAEs leading to study drug discontinuation, related TEAEs, related SAEs and Deaths.
- Incidence of AEs (AEs including TEAEs, SAEs, related TEAEs, related SAEs, TEAEs leading to study treatment discontinuation, AESIs and deaths)
- TEAEs overall and by system organ class and preferred term

This document is confidential.

- TEAEs by severity (Mild, Moderate, Severe), overall and by system organ class and preferred term
- TEAEs by relationship to study treatment (unrelated vs. related), overall and by system organ class and preferred term
- TEAEs leading to study drug discontinuation, overall and by system organ class and preferred term
- TEAEs leading to death, overall and by system organ class and preferred term
- Serious Adverse Events, overall and by system organ class and preferred term
- AESIs by severity (Mild, Moderate, Severe), overall and by preferred term
- AESIs by relationship to study treatment (unrelated vs. related), overall and by preferred term
- SUSARs, overall and by system organ class and preferred term

AEs possibly related and related to study medication will be combined for the "related" summaries.

If a patient met the same AE more than one time, AE will be counted only once with the maximum of severity.

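### A same-day event whose preferred term is broad-only in all three hypersensitivity SMQs, and which does not meet the anaphylaxis algorithm, falls in none of the immediate hypersensitivity searches

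*SAP*

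**What the plan says.** SAP 10.5.4 sets the scope first: "Potential hypersensitivity reactions will be determined using the following Standardised MedDRA Query (SMQs): anaphylactic reaction, hypersensitivity, and angioedema". That sentence is not limited to narrow terms. It then splits the topic by timing. "Potential hypersensitivity will be categorized as immediate (i.e., occurring the same day as drug administration") is one category. The other is "non-immediate (i.e., occurring after the day of study drug administration but prior to subsequent drug administration").

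The immediate list has three searches:

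- Search 1: "1) combined narrow/algorithmic search (that is, any narrow term from any one of the SMQs, or anaphylaxis algorithm").
- Search 2: narrow terms only, shown separately for each SMQ.
- Search 3: "3) TEAEs (occurring on the day of study drug administration) by PT not in any of the 3 SMQs".

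The non-immediate list also has three. The first is a combined narrow search, without the algorithm. The second is a narrow search by SMQ. The third is "3) broad search (that is, any narrow or broad term) by SMQ".

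The SAP does not define the anaphylaxis algorithm and does not say why the two lists differ. Separately, SAP 10.1 plans a table of "TEAEs overall and by system organ class and preferred term" and puts all AEs in listings.

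**The concern.** Only the non-immediate list contains a broad search. In the immediate list, the third search is aimed at terms outside the SMQs altogether. So same-day events with no link to any SMQ are tabulated, and same-day events with a narrow term are tabulated, but a class between them is not: events whose term an SMQ does list, but only as broad.

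The immediate category exists to show reactions close in time to an injection. An event with a broad SMQ term on an injection day meets the section's own description of potential hypersensitivity, yet it would be missing from the summary built to show it. A reader of the report could take the immediate and non-immediate outputs as a complete split of the topic, which they would not be.

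**Working it through.** The plan gives no figure to reproduce, and no event counts enter, so the check is one of set logic. The inputs are the six search definitions in SAP 10.5.4. Each preferred term belongs to one of three classes: narrow in at least one of the three SMQs; broad-only (broad in at least one, narrow in none); or in none of the SMQs. Each event either meets the anaphylaxis algorithm or does not.

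The rules are:

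- Immediate 1: narrow, or algorithm met. Immediate 2: narrow. Immediate 3: in no SMQ.
- Non-immediate 1: narrow. Non-immediate 2: narrow. Non-immediate 3: narrow or broad-only.

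Running every combination through them gives:

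| Term class | Algorithm met | Same-day searches that catch it | Later searches that catch it |
|---|---|---|---|
| Narrow in at least one SMQ | No | 1, 2 | 1, 2, 3 |
| Narrow in at least one SMQ | Yes | 1, 2 | 1, 2, 3 |
| Broad-only | No | none | 3 |
| Broad-only | Yes | 1 | 3 |
| In no SMQ | No | 3 | none |
| In no SMQ | Yes | 1, 3 | none |

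The third row is the gap. A broad-only term is not narrow, so it fails searches 1 and 2. It is in an SMQ, so search 3 excludes it. The last two rows leave no comparable gap: a term outside the SMQs on a later day is outside the topic as the section defines it.

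Two neighbouring cases are not in the gap. An event that meets the algorithm enters through search 1, where the algorithm is an alternative to a narrow term. A term that is broad in one SMQ but narrow in another counts as narrow and enters through searches 1 and 2.

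No other part of the SAP closes the gap. Sections 10.5.1, 10.5.2, 10.5.3 and 10.5.5 refer to a separate sponsor document on safety topics for their term definitions; 10.5.4 does not. Section 10.5.2 tabulates narrow and broad terms separately for opportunistic infections, so using broad terms is already part of this plan's practice.

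With a broad search by SMQ added to the immediate list, the third row goes from no search to one.

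**The case against.** **The wording may be loose rather than wrong.** Search 3 follows two narrow searches and may have been meant as terms outside the narrow scope of the SMQs. That reading would close the gap. It may be what the authors intended, but the text does not say it, and the non-immediate list in the same section treats broad terms as part of an SMQ search. A programmer following the text would exclude them.

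**No data are lost.** This stands. The events are counted in the SOC and preferred-term tables. All AEs are listed (SAP 10.1), AE start dates are collected (Protocol 10.6.2), and patients report administration dates (Protocol 9.3). Serious, related and discontinuation-causing events have their own tables, and injection site reactions have a separate summary (SAP 10.5.5). What is missing is a grouped display that ties these events to the injection day.

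**The stakes are limited.** This also stands. Hypersensitivity is not a designated AESI in Protocol 10.6.1, the output is descriptive, and in the Induction Period the same searches apply to both arms. Equal application does not fill the gap, though: a difference between arms confined to same-day broad-only terms would not show in this topic.

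**Stronger readings that the documents do not support.** A reader might infer that every same-day event with a broad SMQ term disappears; the two neighbouring cases in the working show otherwise. A reader might also try to size the loss from the share of injection days, which is 8 of 112 days in the Induction Period before the Week 16 dose (8/112 = 7.1%), or suppose that nearly all acute reactions would be missed. The first is a share of days, not of events. The second holds only for reactions already assumed to be same-day, broad-only and outside the algorithm; acute reactions with a narrow term, or meeting the algorithm, are kept.

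**Conclusion.** The point holds in a bounded form. Followed as written, SAP 10.5.4 leaves out of every planned hypersensitivity summary those same-day TEAEs whose term is broad-only across all three SMQs and which do not meet the anaphylaxis algorithm, while the same term later in the dosing interval is shown.

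The number of patients affected is unknown. The documents give no event rates, no term lists for the SMQs and no definition of the algorithm, so no range is offered. The conclusion rests on two things: the literal reading of search 3, and the existence of some broad-only terms, which the plan's own distinction between narrow and broad searches presupposes. No efficacy result and no general AE count changes. It is an inconsistency in one descriptive safety output, worth correcting because it falls on injection days and is cheap to remove.

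**What to change.** Make one of two changes to the immediate list in SAP 10.5.4:

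- Add a fourth search, by SMQ, that takes broad as well as narrow terms, matching the third non-immediate search. This is the cleaner choice: the two lists become parallel and the events stay grouped by SMQ.
- Or reword search 3 to take all same-day TEAEs, by preferred term, that searches 1 and 2 have not captured. This closes the gap too, but mixes broad SMQ terms with same-day terms that no SMQ lists.

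If search 3 was meant to exclude only narrow-scope terms, say so explicitly, which has the same effect as the second option for broad-only terms. In either case, define the anaphylaxis algorithm or cite its source, since it decides which broad-only events search 1 catches.

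The cost is one line of SAP text and at most one more table from data already coded. The downside is some non-specific terms in that one descriptive table.

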10.5.5. Injection Site Reactions (ISR)

Injection site reactions (ISRs) are AEs localized to the immediate site of the administration of a drug. The evaluation of study drug related ISRs will be through the unsolicited reporting of ISR TEAEs. Injection site reactions will be defined using the MedDRA High Level Term (HLT) of ISR, excluding certain PTs related to joints as described in the Almirall Safety Topics of Interest.

A summary table of TEAE of ISR overall and by PT will be displayed.

This document is confidential.

10.5.6. Malignancies

Malignancies will be defined using PTs from the Malignant tumors SMQ and summarized separately for the 2 categories: Non-melanoma skin cancer (NMSC) and Malignancies excluding NMSC.

10.5.7. Atopic Dermatitis Exacerbation

A summary table of TEAE of atopic dermatitis exacerbation will be displayed. Atopic dermatitis exacerbation will be defined using the following PTs:

- Dermatitis atopic
- Eczema
- Rebound atopic dermatitis
- Rebound eczema
- Dermatitis allergic
- Erythrodermic atopic dermatitis

This document is confidential.

11. Changes from Analysis Planned in Protocol

The reasons for exclusion will be presented in the listings of protocol deviations instead of summarizing in table.

Any analysis described as 'by visit' in the protocol are described as 'by week' in this SAP and in the tables and figures.

Following 2 Secondary Endpoints are added in this SAP.

- Percentage of patients achieving IGA 0/1 and 2-point improvement by week up to Week 16.
- Percentage of patients achieving a 4-point improvement Pruritus NRS by week up to Week 16.

This document is confidential.

12. Reference List

This document is confidential.

13. Programming Considerations

All tables, figures, listings (TFLs), and statistical analyses will be generated using SAS for Windows, Release 9.4 or higher (SAS Institute Inc., Cary, NC, USA). Computer-generated table, listing and figure output will adhere to the following specifications.

13.1. General Considerations

- One SAS program can create several outputs, or a separate SAS program will be created for each output
- One output file can contain several outputs, or each output will be stored in a separate file
- Output files will be delivered in Word format or portable document format pdf
- Numbering of TFLs will follow ICH E3 guidance

13.2. Table, Figure, and Listing Format

13.2.1. General

- All TFLs will be produced in landscape format on A4 paper size, unless otherwise specified.
- All TFLs will be produced using the Courier New font, size 8 which is the smallest acceptable point size for the Regulatory Authorities.
- The data displays for TFLs will have a minimum blank 1-inch margin on all 4 sides.
- Headers and footers for figures will be in Courier New font, size 8 which is the smallest acceptable point size for the Regulatory Authorities.
- Legends will be used for all figures with more than one variable, group, or item displayed.
- TFLs will be in black and white (no color), unless otherwise specified.
- Specialized text styles, such as bolding, italics, borders, shading, and superscripted and subscripted text, will not be used in the TFLs, unless otherwise specified. On some occasions, superscripts 1, 2, or 3 may be used (see below).
- Only standard keyboard characters will be used in the TFLs. Special characters, such as non-printable control characters, printer-specific, or font-specific characters, will not be used. Hexadecimal-derived characters will be used, where possible, if they are appropriate to help display math symbols (e.g., μ). Certain subscripts and superscripts (e.g., cm^2 , C_{max}) will be employed on a case-by-case basis.
- Mixed case will be used for all titles, footnotes, column headers, and programmer-supplied formats, as appropriate.

13.2.2. Headers

- All output will have the following header at the top left of each page:
- ALMIRALL S.A. Protocol M-17923-30 ADvantage PPD [redacted] Health study number [redacted] (CC1 [redacted])

This document is confidential.

- Draft/Final Run
- All output will have Page n of N at the top or bottom right corner of each page. TFLs are internally paginated in relation to the total length (i.e., the page number will appear sequentially as page n of N, where N is the total number of pages in the table)
- The date the output was generated will appear along with the program name as a footer on each page

13.2.3. Display Titles

- Each TFL will be identified by the designation and a numeral. (i.e., Table 14.1.1). A decimal system (x.y and x.y.z) are used to identify TFLs with related contents. The title will be centered. The analysis set will be identified on the line immediately following the title and will be enclosed in parenthesis. The title and table designation will be single spaced. A solid line spanning the margins will separate the display titles from the Column headers. There will be one blank line between the last title and the solid line.

Table x.y.z
First Line of Title
Second Line of Title if Needed
(Full Analysis Set)

13.2.4. Column Headers

- Column headings will be displayed immediately below the solid line described above in initial upper-case characters.
- In the case of efficacy tables, the variable (or characteristic) column is on the far left followed by the treatment group columns and total column (if applicable). P-values may be presented under the total column or in separate p-value column (if applicable). Within-treatment comparisons may have p-values presented in a row beneath the summary statistics for that treatment
- For numeric variables, include 'unit' in column or row heading when appropriate
- Analysis set sizes will be presented for each treatment group in the column heading as (N=xx) (or in the row headings, if applicable). This is distinct from the 'n' used for the descriptive statistics representing the number of patients in the analysis set
- The order of treatments in the tables and listings will be Placebo first in the case of placebo controlled studies and Active comparators first in the case of active comparator trials, followed by a total column (if applicable)

13.2.5. Body of the Data Display

13.2.5.1. General Conventions

Data in columns of a table or listing are formatted as follows:

- Alphanumeric values will be left-justified;

This document is confidential.

- Whole numbers (e.g., counts) will be right-justified; and
- Numbers containing fractional portions will be decimal aligned.

13.2.5.2. Table Conventions

- Units will be included where available
- For categorical parameters, all categories will be presented in the table, even if n=0 for all treatment groups in a given category. For example, the frequency distribution for symptom severity would appear as:

Severity Rating	N
severe	0
moderate	8
mild	3

Where percentages are presented in these tables, zero percentages will not be presented and so counts of 0 will be presented as 0 and not as 0 (0%).

- An Unknown or Missing category will be added to each parameter for which information is not available for 1 or more patients
- Unless otherwise specified, the estimated mean and median for a set of values will be printed out to 1 more significant digit than the original values, and standard deviations will be printed out to 2 more significant digits than the original values. The minimum and maximum will report the same significant digits as the original values. For example, systolic blood pressure will be presented as follows:

N	XX
Mean	XXX.X
Std Dev	X.XX
Median	XXX.X
Minimum	XXX
Maximum	XXX

- P-values will be output in the format: '0.xxx', where xxx is the value rounded to 3 decimal places. Every p-value less than 0.001 will be presented as <0.001. If the p-value are less than 0.0001, then present as <0.0001. If the p-value is returned as >0.999, then present as >0.999
- Percentage values will be printed to one decimal place, in parentheses with no spaces, one space after the count (e.g., 7 (12.8%), 13 (5.4%)). Unless otherwise noted, for all percentages, the number of patients in the analysis set for the treatment group who have an observation will be the denominator. Percentages after zero counts will not be displayed and percentages equating to 100% will be presented as 100%, without decimal places
- Tabular display of data for medical history, prior/concomitant medications, and all tabular displays of adverse event data will be presented by the body system, treatment class, or SOC with the

This document is confidential.

highest occurrence in the active treatment group in decreasing order, assuming all terms are coded. Within the body system, drug class and SOC, medical history (by preferred term), drugs (by ATC1 code), and adverse events (by preferred term) will be displayed in decreasing order. If incidence for more than 1 term is identical, they will then be sorted alphabetically. Missing descriptive statistics or p-values which cannot be estimated will be reported as '-'

- The percentage of patients will normally be calculated as a proportion of the number of patients assessed in the relevant treatment group (or overall) for the analysis set presented. However, careful consideration is required in many instances due to the complicated nature of selecting the denominator, usually the appropriate number of patients exposed. Details will be described in footnotes or programming notes, as necessary
- For categorical summaries (number and percentage of patients) where a patient can be included in more than one category, a footnote or programming note will be added describing whether the patient is included in the summary statistics for all relevant categories or just 1 category as well as the selection criteria
- Where a category with a subheading (such as system organ class) has to be split over more than one page, output the subheading followed by '(cont)' at the top of each subsequent page. The overall summary statistics for the subheading should only be output on the first relevant page

13.2.5.3. *Listing Conventions*

- Listings will be sorted for presentation in order of treatment groups as above, patient number, visit/collection day, and visit/collection time
- Missing data will be represented on patient listings as either a hyphen ('-') with a corresponding footnote ('- = unknown or not evaluated'), or as 'N/A', with the footnote 'N/A = not applicable', whichever is appropriate
- Dates will be printed in SAS DATE9.format ('DD_MMM_YYYY': 01JUL2000). Missing portions of dates will be represented on patient listings as dashes (–JUL2000). Dates that are missing because they are not applicable for the patient will be output as 'N/A', unless otherwise specified
- All observed time values will be presented using a 24-hour clock HH:MM or HH:MM:SS format (e.g., 11:26:45, or 11:26). Time will only be reported if it was measured as part of the study
- Units will be included where available

13.2.5.4. *Figure Conventions*

- Unless otherwise specified, for all figures, study visits will be displayed on the X-axis and endpoint (e.g., treatment mean change from Baseline) values will be displayed on the Y-axis

13.2.6. *Footnotes*

- A solid line spanning the margins will separate the body of the data display from the footnotes.
- All footnotes will be left justified with single-line spacing immediately below the solid line underneath the data display

This document is confidential.

- Footnotes will always begin with 'Note:' if an informational footnote, or 1, 2, 3, etc. if a reference footnote. Each new footnote will start on a new line, where possible
- Patient specific footnotes are avoided, where possible
- Footnotes will be used sparingly and add value to the TFL. If more than six lines of footnotes are planned, then a cover page is strongly recommended to be used to display footnotes, and only those essential to comprehension of the data will be repeated on each page
- The last line of the footnote section will be a standard source line that indicates the name of the program used to produce the data display, the date the program was run, and the listing source (i.e., 'Program : myprogram.sas Listing source: 16.x.y.z')
- Sources and/or cross-references in footnotes will use the keyword prefix (in singular form) for each reference and will be separated by a comma when multiple cross-references are displayed

Example

Listing source: Listing 16.2.4.1.1, Listing 16.2.4.1.2, Listing 16.2.4.2.1

This document is confidential.

14. Quality Control

SAS programs are developed to produce output such as analysis data sets, summary tables, data listings, figures or statistical analyses. An overview of the development of programs is detailed in **PPD** **Developing Statistical Programs SOP (3907)**.

PPD **Developing Statistical Programs SOP (3907)**, **Conducting the Transfer of Biostatistical Deliverables SOP (3908)** and the **SAS Programming and Validation Plan** describes the quality control procedures that are performed for all SAS programs and output. Quality control is defined here as the operational techniques and activities undertaken to verify that the SAS programs produce the output by checking for their logic, efficiency and commenting and by review of the produced output.

This document is confidential.

15. Appendices

